Outcome measures in this study were created for this evaluation and are not based on already-validated scales. Using the local evaluation baseline survey, we will generate a correlation matrix between items in a given construct to ensure that theoretically related items are also empirically related in our data set. Items that are not strongly correlated with other items in a construct will be removed as necessary. Factor analysis will be used to ensure that all construct items hang together (using an alpha of 0.60 or higher as the threshold). We will then create a composite measure by taking an average of the scores on each non-missing item in the construct. For composite measures, a change score will be calculated between a participant's pre-program composite score and six-month-post-enrollment follow-up composite score. If construct items do not meet the 0.60 threshold, that outcome will be removed. An alpha value of 0.60 is the minimally acceptable value that will be used for scale construction.

We will create a composite score by taking the average of multiple individual items. For these composite measures, our plan is to use 20% as a threshold for allowable missing items. This plan is contingent on the final distribution of missing data in our dataset. With a 20% threshold, if a respondent is missing more than 1 item used for creating the employment construct or more than 2 items for creating the financial construct, the respondent will be assigned a missing value for that construct. We will not impute truly missing values for outcomes. To create a construct score, the average will be divided by the number of non-missing values in the construct.

Table 1. Description of outcome measures used to answer impact analysis primary research questions

Research question #	Outcome name	Description of the outcome measure and its properties	Source of the measure	Timing of measure
1	Employment Attitudes	
The outcome measure is a scale (value range of 1=strongly disagree to 5=strongly agree) calculated as the average of eight survey items related to employment attitudes.
 
Sample item: I have the skills I need to get a decent job.
	Local evaluation follow-up-survey	Six months after program enrollment

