The data for this impact evaluation comes from surveys of study participants. Participants are surveyed at three different time points throughout the study-baseline, post-survey, and six-month post-enrollment follow-up. The process and timing for data collection are the same for all study participants, regardless of study condition assignment. Wave 1 of data collection, which includes completion of the nFORM Applicant Characteristics Survey, the nFORM Healthy Marriage Adult Program Entrance Survey, and the local evaluation baseline survey, happens during orientation before any primary workshop hours have been delivered. Wave 2 of data collection, which includes the nFORM Healthy Marriage Adult Program Exit Survey and the local evaluation post-survey, happens six weeks after program enrollment for both study groups. Wave 2 of data collection happens immediately following the final primary workshop session for the in-person group, but since the on-demand mode is self-paced, the amount of time that has elapsed between curriculum completion and wave 2 of data collection six weeks post-enrollment can vary for on-demand group participants. For example, if a participant in the on-demand delivery group completes the TYRO curriculum two weeks after enrollment, then four weeks will have elapsed between program completion and administration of the exit survey.

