To increase follow-up response rates and with the approval of OFA, alternative follow-up data collection procedures were developed by the RIDGE and evaluation teams for one service site that enrolls most of the impact study participants at about 78%, Franklin CBCF. Many impact study participants from the Franklin CBCF service site go on to participate in a Department of Labor initiative immediately following their release from prison. As part of this initiative, participants are bussed from the Franklin CBCF to an American Jobs Center. TYRO Couples RCT participants who are part of this initiative are invited to complete a paper follow-up survey on the Thursday prior to the bus taking participants to the American Jobs Center the following Monday morning. Eligible participants who completed the survey will be handed a physical \$50 gift card upon boarding the bus. This follows guidelines of prisons where no monetary incentives can be administered on the premises. To be eligible for the follow-up survey, participants must have a signed consent form on file and have taken either the nFORM entrance survey or the local evaluation baseline survey. Evaluation staff will coordinate with program staff to ensure only those who are eligible for the follow-up survey are offered it. Paper surveys will be sealed in an envelope where they are given to a team member certified in protecting human research participants to enter the surveys into Qualtrics. Paper surveys are to be kept in locked storage at RIDGE offices and will be stored for a minimum of three years before being destroyed in accordance with IRB guidelines. This process is set to begin in May 2024.

Table 5. Key features of the data collection

Study group	Data source	Timing of data collection	Mode of data collection	Party responsible for data collection	Start and end date of data collection
Intervention (on-demand)	Survey Wave 1 (nFORM baseline and local evaluation baseline surveys)	Immediately following informed consent and randomization during orientation (within 1-2 weeks of enrollment)	In-person paper survey	RIDGE Staff	April 11, 2023 – November 30, 2024
	Survey Wave 2 (nFORM exit and local evaluation post-surveys)	Six weeks after program enrollment	In-person paper survey	RIDGE Staff	May 23, 2023 (or February 2023 for pilot cohort) – January 11, 2025

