Because outcome measures for this impact study are constructed from survey items from both nFORM and the local evaluation surveys, survey nonresponse on either the nFORM baseline survey, local evaluation baseline survey, nFORM exit survey, local evaluation post survey, or local evaluation follow-up survey can lead to sample attrition. Survey response rates are monitored on an ongoing basis through bi-weekly CQI reports produced by the evaluation team using the nFORM Survey Completion Summary operational report and Qualtrics response data export feature. Response rates are calculated by dividing the number of participants who responded to each survey by the number of participants who were eligible to respond to that survey up to that time point. If CQI reports show that survey response rates are below intended targets, the CQI team brainstorms and implements strategies to increase response rates to minimize sample attrition caused by survey nonresponse. Reasons for survey nonresponse, to the degree that they are known, will be reported in the CONSORT diagram. Individuals with survey nonresponse at the follow-up time point will not be included in the analytic sample; the analysis for each outcome will use complete case data.

Item nonresponse

Item nonresponse can also lead to sample attrition for particular outcome measures if participants skip survey items that are aligned with the research questions for this study. Item nonresponse is calculated by dividing the number of participants who respond to a survey item by the number who were eligible and able to answer a question based on skip/display logic. As stated in the data preparation section above, respondents taking paper surveys may violate skip/display logic, and invalid responses will be dropped before item-level response rates are calculated. We will also note what proportion of the sample skipped out of the relationship and employment attitude questions to give context to the item nonresponse.

Constructed outcome measures

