Each of the outcomes for the primary research questions for this study are constructed averages using multiple, related survey items. Sufficiently high item nonresponse among items used to construct outcome measures will lead to sample attrition for that outcome. The evaluation team plans to use an 80% threshold as the cutoff for constructed measures; respondents who answer less than 80% of survey items associated with a constructed measure will be dropped from the analysis for that outcome. The constructed average for each participant who has answered at least 80% of associated survey items will be calculated by dividing the sum of their survey answers by the number of items they answered. For example, if a participant answers 8 out of 10 survey items associated with a construct, their average for that outcome measure will be the sum of their 8 answers divided by 8. The evaluation team does not plan to use imputation for multi-item constructed outcomes with 20 percent or fewer missing items. A sensitivity analysis will be conducted to see if and how results would change with a 70% threshold cutoff instead of an 80% cutoff.

2. Attrition and analytic sample

The analytic sample for each outcome construct identified in Table 2 will consist of study participants who have a non-missing value at baseline and follow-up time points for that construct (complete case). The size of the analytic sample may vary by outcome measure based on the prevalence of item non-response missing data at the baseline and follow-up surveys for the items used to create those composite measures. For attitudinal outcomes related to economic stability, and finances, all respondents with complete case data will be included in the analytic sample. For relationship behavior outcomes, participants will be included in the analytic sample if they report being in a committed relationship at the time the survey was administered (i.e., do not choose 'no' for the skip logic question 'Are you currently in a committed romantic relationship?'). Because this skip logic was added to the local evaluation surveys belatedly (in October 2023), this condition will only apply to those respondents who took a survey with this skip logic. For those respondents who took a survey before this relationship skip logic was added, all participants who have complete case data will be included in the analytic sample in response to the secondary research question.

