All outcome measures for this study are constructed averages calculated using a number of theoretically and empirically related survey items. As mentioned in the previous section, a respondent who answers some but not all survey items in a given outcome construct will have their outcome value assigned as missing if they do not respond to at least 80% of the items in the construct. We will not impute missing baseline or outcome data for our analyses. Based on the recommendation from ACF, we will use the cautious attrition threshold from the What Works Clearinghouse (WWC) to assess whether attrition can be considered high or low.

Assessment of baseline equivalence

Per the WWC's standards, we will use effect sizes (i.e., standardized mean differences), to examine the baseline equivalence between the study groups. Effect size is defined as the difference between the intervention group mean and the comparison group mean, divided by the pooled standard deviation. We will calculate the effect size for demographic characteristics (such as gender, age, and race/ethnicity, as reported on the nFORM Applicant Characteristics Survey) and each baseline outcome of interest depending on the type of variable: Hedge's g , for continuous variables; and Cox's index, for dichotomous variables. We can determine baseline equivalence by comparing each outcome's effect size using the WWC standard, which suggests that if the corresponding effect size is 0.05 or less in absolute value, it is considered "small," and we can conclude that it satisfies baseline equivalence without statistical adjustment. However, if the effect size falls between 0.05 and 0.25, it is considered "moderate," and it will require a statistical adjustment to meet baseline equivalence (we will use statistical adjustments such as regression adjustments or matching/weighting). Lastly, in the case that the effect size is greater than 0.25, it will be considered "large", which shows that the differences at baseline are too large to meet WWC standards, even with statistical adjustments. In that case, we will apply appropriate caveats to any interpretation of the results.

Condition crossover

At the primary RCT enrollment site, Franklin CBCF, condition crossover is not possible due to restrictions put in place when designing the implementation of the two delivery formats. If a participant who was

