Next, we will conduct an analysis to see how outcome construct measures change if we use mean imputation to replace missing items in the multi-item scales used to create our outcome variables. This is the mean based on observed values from the rest of the sample for that item. The current plan is not to use any imputation for outcome measures, including constructed outcomes from multiple survey items, and instead to make the denominator for the calculation of the average score be equal to the number of non-missing items in that construct.

Finally, we plan to conduct a sensitivity analysis regarding the timing of the follow-up survey. Given changes in follow-up data collection protocol at Franklin CBCF, we anticipate that some respondents will have taken their paper follow-up survey earlier than intended. The sensitivity analysis will repeat our analyses using only people who completed their follow-up survey within the intended data collection window (5-7 months post-enrollment).

5. Analyses addressing secondary research questions

The analytic approach for answering the secondary research question about partner relationship behaviors will be the same as the approach taken for the primary research questions.

Figure A.3. CONSORT diagram for individual clients, for studies in which consent occurred before assignment

Eligible for 6-month post-enrollment follow-up (n = 206)

To be eligible, a participant must have provided consent and taken either the nFORM baseline or local evaluation baseline survey

Completed follow-up (n = 64)

Data collection: July 1, 2023-July 22, 2024

Reasons for non-completes (n = 1) (that can be accounted for)

Consent revoked (n = ___), declined survey (n = ___), deceased (n = ___), dropped out (n = 7), moved (n = ___), incarcerated (n = 1)

Eligible for 6-month post-enrollment follow-up (n = 190)

To be eligible, a participant must have provided consent and taken either the nFORM baseline or local evaluation baseline survey

Completed follow-up (n = 52)

Data collection: July 1, 2023-July 22, 2024

Reasons for non-completes (n = 1) (that can be accounted for)

Consent revoked (n = ___), declined survey (n = ___), deceased (n = ___), dropped out (n = 4), moved (n = ___), incarcerated (n = 1)

Figure A.4. Survey items linked to research questions

Measure	Item Response	Are these items linked to a primary research question?	Are these items linked to a secondary research question?
Partner relationship beliefs 8 items			No

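### Some randomised participants with an observed primary outcome are dropped because their baseline composite is missing; keeping them is a cheap improvement, though the number affected is not given and may be small

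*Combined protocol and SAP*

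**What the plan says.** **Who is followed up.** Under the Franklin CBCF procedure in section C.2, a participant needs a signed consent form and must "have taken either the nFORM entrance survey or the local evaluation baseline survey". Figure A.3 gives the same condition for both arms: "a participant must have provided consent and taken either the nFORM baseline or local evaluation baseline survey". These are separate instruments within Wave 1: "the nFORM Healthy Marriage Adult Program Entrance Survey, and the local evaluation baseline survey, happens during orientation".

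**Where the scores come from.** Table 1 gives the source of both primary outcomes as "Local evaluation follow-up-survey". For the baseline side, section A.3 says "Using the local evaluation baseline survey, we will generate a correlation matrix between items in a given construct". Section D.1 (survey nonresponse) differs: "outcome measures for this impact study are constructed from survey items from both nFORM and the local evaluation surveys".

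**Who is analysed.** Section D.2 limits the analytic sample to "study participants who have a non-missing value at baseline and follow-up time points for that construct". That sentence refers to Table 2, which holds the secondary outcomes, but the same paragraph applies complete-case selection to the economic and financial attitudes, so the primary outcomes are covered. Section D.2 adds: "We will not impute missing baseline or outcome data for our analyses". A composite counts as missing when fewer than 80% of its items are answered.

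**How baseline is used.** Section D.3 regresses the follow-up score on assignment, the baseline score and other covariates. Section A.3 also plans a change score. Section D.2 uses baseline outcomes for the equivalence check and calls for statistical adjustment when the difference lies between 0.05 and 0.25 SD.

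**The concern.** The eligibility rule and the analysis rule do not fit together. A participant with only the nFORM baseline is tracked, surveyed and paid the incentive, and may return a full primary outcome. That outcome is then set aside because a covariate is absent. The same happens to someone who completes the follow-up scale but skipped too many items on the baseline scale.

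A randomised comparison of follow-up scores does not need every participant's baseline score. What is at stake is avoidable attrition. Follow-up return was low at the July 2024 data pull, and section D.2 will judge attrition against the cautious WWC threshold, so each observed outcome removed for this reason makes that position worse.

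**Working it through.** **1. The rules side by side.** The plan states no figure for the number affected, so the first check is of logic.

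| Step | Participant with only the nFORM baseline |
|---|---|
| Eligible for follow-up (C.2, Figure A.3) | Yes |
| Can supply the primary outcome (Table 1) | Yes |
| Has a baseline composite (A.3: local baseline survey) | No |
| Baseline imputed (D.2) | No |
| In the analytic sample (D.2) | No |

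Section D.4 plans three sensitivity analyses: a 70% item threshold, item-mean imputation, and restriction by survey timing. None clearly retains a participant with no local baseline survey.

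**2. The item-level route.** Employment has eight items. Answering 6 gives 6/8 = 75%, which fails 80% and passes 70%; answering 5 gives 62.5%, which fails both. Finance has seven items. Answering 5 gives 5/7 = 71.4%, which fails 80% and passes 70%; answering 4 gives 57.1%, which fails both. The 70% analysis therefore recovers participants with two items missing but not those with three or more. The item-mean analysis is worded for the scales behind the outcome variables, and the plan does not say whether baseline items are included. Section A.3 also sets financial scores to missing only when more than two items are missing, which does not match 80% of seven items.

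**3. Follow-up so far (Figure A.3).** 64/206 = 31.1% and 52/190 = 27.4%; together 116/396 = 29.3%.

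**4. Possible counts.** Let q be the share of follow-up responders with no baseline composite (assumed).

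| q | Dropped from 116 | Analysable share of 396 | Dropped if 768 respond |
|---|---|---|---|
| 5% | 6 | 27.8% | 38 |
| 10% | 12 | 26.4% | 77 |
| 20% | 23 | 23.4% | 154 |

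At q = 2%, about 2 of 116 or 15 of 768 would be dropped.

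**5. Effect on the standard error.** Let r be the baseline–outcome correlation (assumed), the outcome variance 1, and n the number of responders per arm.

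- Dropping them: variance ∝ (1 − r²) / [n(1 − q)].
- Keeping them with a constant fill and an indicator in ordinary regression: variance ∝ [(1 − q)(1 − r²) + q] / n.
- SE ratio, keep to drop: √{(1 − q)[(1 − q) + q/(1 − r²)]}.

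| q | r = 0.4 | r = 0.6 |
|---|---|---|
| 1% | √0.9919 = 0.996 | √0.9956 = 0.998 |
| 2% | √0.9837 = 0.992 | √0.9910 = 0.996 |
| 5% | √0.9590 = 0.979 | √0.9767 = 0.988 |
| 20% | √0.8305 = 0.911 | √0.8900 = 0.943 |

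The reduction is 1.2% to 8.9% for q of 5–20%, and under 1% for q of 1–2%. Summing the information from the two subsets instead gives ratios of 0.909–0.984 for q of 5–20%. That assumes optimal weighting, which ordinary regression does not apply.

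**The case against.** **The loss may be negligible.** All Wave 1 surveys are taken on paper at the same orientation, and the local baseline survey carries a consent item, so few people may have completed only the nFORM survey. This stands. A reader might infer from the 29.3% return that the baseline rule is a major cause of loss. The documents do not support that: they give no count, the return figure reflects missing follow-up surveys, and it comes from an interim pull soon after the Franklin procedure was due to start in May 2024.

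**Baseline does more than add precision.** A reader might infer that the score is purely a precision covariate, so that requiring it adds nothing to validity. Section D.2 contradicts this, since baseline outcomes feed the equivalence check and any adjustment for imbalance. With heavy outcome loss, responders cannot be assumed to be an intact randomised comparison. This stands, and it is why the complete-case analysis should stay in the report.

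**The choice is open and partly tested.** Section D.1 lists baseline nonresponse as a source of attrition, so nothing is concealed, and two sensitivity analyses bear on item nonresponse. Neither clearly reaches participants with no local baseline survey.

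**The remedy rests on unsettled timing.** Sections C.1 and C.2 place the baseline surveys in orientation, before assignment is announced, whereas Table 5 places Wave 1 after randomisation. If some baseline surveys follow disclosure, missingness could depend on assignment and the indicator could bias the estimate. This stands as a condition on the fix.

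**The item source is stated two ways.** If nFORM carried the primary items, contrary to Table 1 and section A.3, the nFORM-only route would weaken. The under-80% route would remain.

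**Conclusion.** The point holds as an avoidable loss. As written, the plan excludes some randomised participants with an observed primary outcome because their baseline composite is missing, either through the absence of a local baseline survey or through too few baseline items answered. The existing sensitivity analyses cover the second route only in part.

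Its size cannot be fixed from the documents. The 1–9% range rests on assumed values (5–20% of responders affected, correlation 0.4–0.6), and the benefit could well be below 1%. A reader might go further and infer that the complete-case estimate is biased; nothing in the documents shows that. This is a cheap improvement to make before analysis. Follow-up nonresponse is the larger problem on the figures given.

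**What to change.** First reconcile three pairs of statements:

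- Table 5 with sections C.1 and C.2, stating whether every baseline survey is completed before assignment is disclosed. The indicator method is valid only if so.
- The change score in section A.3 with the regression of the follow-up score in section D.3. A change score cannot be formed for participants without a baseline.
- The item source in section D.1 with Table 1.

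Then, in D.2 and D.3:

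- Define the primary sample as all randomised participants with a valid follow-up composite.
- Where the baseline composite is missing, set it to the pooled mean of the observed baseline scores and add a missing-baseline indicator to the model.
- Leave outcomes un-imputed.
- Report the current complete-case analysis alongside, with the equivalence check on observed baselines, and give the number of participants retained by the wider definition.

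The cost is some SAP wording, one model term and one extra reported analysis. The downside must be stated in the report: participants retained without a baseline score are not baseline-adjusted and fall outside the equivalence check.
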